9.3 Analytic plan for primary objective

9.3.1 Pilot Portion: Each evaluable patient will be assessed for “*concerning toxicities*” and “*serious toxicities*”. If 6 or more patients demonstrate a “*concerning toxicity*” or 1 or more patients experience a “*serious toxicity*”, the therapy will be considered not feasible to deliver and one dose reduction will occur. If 6 or more patients demonstrate a “*concerning toxicity*” or 1 or more patients experience a “*serious toxicity*” on the dose reduced schedule, the intervention will be considered too toxic and the protocol will be terminated. Inevaluable patients will be replaced.

9.3.2 Randomized Portion:

After the acceptable glyburide dose has been established, the randomized portion will commence. No formal interim monitoring will take place and study analysis will be done when all 20 randomized patients are accrued in each treatment regimen. The results from this portion of the trial will be used as a screening mechanism for assessing whether glyburide should be studied in a formal randomized trial. The number of patients who experience treatment successes will be compared between the two regimens using the

exact test of proportions. If this test yields a one-sided test of equality of proportions of treatment success obtains a p-value of 0.30 or less, glyburide treatment will be considered as sufficiently interesting for further study. Otherwise, glyburide will be considered not interesting for further development. We acknowledge that the type 1 error rate of 0.30 is liberal, and note that this was chosen based on the preliminary efficacy aspect of the study; post-analysis power calculations may be performed.

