group, who will not be allowed to receive steroids unless they experience a clinical failure. As noted above, this selection design will use a type I error rate of 30%. A type I error rate of 30% is used because given the expected accrual in combination with limited funding available for the study, our goal is to determine if there is a signal for treatment success that would generate sufficient interest to escalate the study idea into a cooperative group setting, where the question of efficacy may be more definitively addressed. If the treatment success rate with glyburide is 75%, glyburide will be identified for further study with probability of 0.80. The power associated with other values for the treatment success probability for Glyburide is demonstrated in the figure below:

We project an inevaluability rate of at most 20%. The study will be completed with the enrollment of approximately 63 patients over an estimated 2 year enrollment period after approval.

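### The 30% type I error is a nominal ceiling: the exact test that matches the stated 0.80 power attains at most 0.215, so part of the chosen allowance goes unused

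*Combined protocol and SAP*

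**What the plan says.** Section 9.3.2 (Randomized Portion) fixes the timing and size of the analysis: "study analysis will be done when all 20 randomized patients are accrued in each treatment regimen". It describes the test as an "exact test of proportions. If this test yields a one-sided test of equality of proportions", and sets the decision rule: if the test "one-sided test of equality of proportions of treatment success obtains a p-value of 0.30 or less", glyburide goes forward. The variant of exact test is not named. The same section then treats the threshold as the error rate: "We acknowledge that the type 1 error rate of 0.30 is liberal".

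Section 9.5.2 repeats the figure as the error rate of the design: "this selection design will use a type I error rate of 30" percent. It justifies the figure by expected accrual and limited funding: "our goal is to determine if there is a signal for treatment success that would generate sufficient interest". It assumes 50% success on placebo and states: "If the treatment success rate with glyburide is 75%, glyburide will be identified for further study with probability of 0.80".

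Neither section separates the nominal p-value threshold from the error rate that the test attains with 20 patients per arm.

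**The concern.** With 20 patients per arm there are only 21 × 21 possible results, so an exact p-value moves in jumps. An exact test run at a nominal 0.30 can have a real false-go probability well below 0.30, and exact tests differ in how far below. The plan states a 30% error and a 0.80 power side by side. A reader would take them as the two operating characteristics of one rule.

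Two things are at stake. First, the team made a deliberate trade: it accepted a liberal error rate in order to see a signal with few patients. If the rule is stricter than 30%, part of that trade is not collected. Second, with the test unnamed, two fair readings of the wording give different go/no-go decisions for some results. That choice should be made before anyone sees the data.

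**Working it through.** **Inputs.** 20 per arm, one-sided test, go if p ≤ 0.30, no interim analysis (9.3.2); placebo success 0.50, glyburide success 0.75, stated power 0.80 (9.5.2).

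**Method.** Let T and C be the numbers of successes on glyburide and placebo, independent Binomial(20, p). For each of the 441 pairs (t, c), the one-sided Fisher p-value is P(X ≥ t), where X is hypergeometric (40 patients, t + c successes, 20 drawn). The go region R is the set of pairs with p ≤ 0.30.

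- Power = sum over R of Bin(t; 20, 0.75) × Bin(c; 20, 0.50).
- Size at a common rate p = sum over R of Bin(t; 20, p) × Bin(c; 20, p), maximized over a grid of p.

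**Step 1: reproduce the plan's power.** The candidate tests at nominal 0.30, one-sided unless noted:

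| Test | Power, 75% vs 50% | Size at 50% | Maximum size |
|---|---|---|---|
| Fisher | 0.802 | 0.215 | 0.215 |
| z with continuity correction | 0.802 | 0.215 | 0.215 |
| Boschloo | 0.865 | 0.250 | 0.298 |
| Barnard (pooled z) | 0.865 | 0.250 | 0.298 |
| Fisher mid-p | 0.881 | 0.318 | 0.318 |
| z, pooled or unpooled | 0.881 | 0.318 | 0.339 |
| Fisher, two-sided | 0.584 | 0.077 | 0.081 |

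The usual normal-approximation formula gives 0.874 one-sided. Among the exact tests, only one-sided Fisher returns the stated 0.80. The continuity-corrected z test gives the same power and size, but it is not an exact test.

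**Step 2: attained error of that rule.** Size is 0.2148 at a common success rate of 0.50, and this is the maximum over all common rates. Unused allowance: 0.30 − 0.2148 = 0.0852, about 8.5 points.

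**Step 3: why the gap arises.** The largest Fisher p-value that passes is 0.2636 (11 vs 8 and 12 vs 9); the next possible value is 0.3025 (3 vs 1 and 19 vs 17). Nothing lies between, so any threshold in that gap gives the same decisions. In effect glyburide must lead by at least 3 successes; the only additions are 2 vs 0 and 20 vs 18. For example, 13 vs 10 gives p = 0.262 (go) and 12 vs 10 gives p = 0.376 (no go).

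**Step 4: what an unconditional exact test would do.** Boschloo uses the Fisher p-value as its statistic and takes the largest cut-off that keeps the maximum size within 0.30.

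- Cut-off 0.3738: maximum size 0.298, near common rates of 31% and 69%. The next cut-off, 0.3756, would give 0.306, which is too large.
- Size at 50% success: 0.250. Power: 0.865, a gain of 0.865 − 0.802 = 0.063.
- Chance of missing a true 75% success rate: 1 − 0.802 = 0.198 with Fisher, 1 − 0.865 = 0.135 with Boschloo.
- Of the 19 possible two-patient leads, Fisher passes 2 and Boschloo 16, so 14 results change from no go to go. One is 15 vs 13 (Fisher p = 0.366, Boschloo p = 0.278). The three that still fail are 10 vs 8, 11 vs 9 and 12 vs 10.
- Passing all 19 would give a size of 0.318, above the plan's limit.

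**The case against.** The strongest reply is that nothing in the plan is wrong. The decision rule is stated as a p-value threshold. Calling that threshold the type I error rate is ordinary usage for a discrete exact test, where alpha is a ceiling. The gap is in the safe direction, the promised power is delivered, and the 20% chance of missing a 75% success rate is already implied by the stated 0.80. This is a screening study, and a false-go risk of 21.5% instead of 30% makes a go decision more credible. All of this stands, and it is why the point is not an arithmetic error.

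A reader might infer more: that the design loses control of its error rate, that the power or the 20 per arm is miscalculated, or that the plan claims an attained error of exactly 30%. The documents support none of these. The ceiling is respected, the power is reproduced, and no attained rate is claimed.

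It is also fair to say that Fisher is back-fitted from the power. The power figure that accompanies 9.5.2 is not visible in the text reviewed and may name the test.

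Finally, moving to Boschloo is a choice, not a correction. It gains power the plan did not ask for, recovers only 0.250 − 0.215 = 0.035 of the unused allowance at the plan's own 50% rate, and treats equal two-patient leads differently. Those are real costs and belong in the decision.

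What the reply does not remove is that none of the exact tests checked has both a 30% attained error and 0.80 power, and that the wording leaves open which test is meant.

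**Conclusion.** The point holds as a clarification and a cheap improvement. The 30% is a nominal threshold and a valid upper bound. If the test is one-sided Fisher, as the stated power indicates, the attained error is at most 0.215 and about 8.5 points of the chosen allowance are unused. If an unconditional exact test was meant, the attained error comes close to 30% (maximum 0.298), but the stated power is too low (0.865, not 0.80). Under either reading the pair of figures needs a sentence of explanation.

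The computation is firm. It assumes 20 evaluable patients in each arm, independent binomial outcomes and the plan's 50% and 75% success rates. The identification of Fisher is an inference. The consequence is modest: no patient numbers change, no error control is lost, and up to about 6 points of power are available if the team wants them.

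**What to change.** Before unblinding, name the exact test in 9.3.2 and state its attained size and power in 9.5.2. There are two acceptable ways to do so.

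1. **Use more of the 30% already chosen.** Suggested wording: *Boschloo's one-sided unconditional exact test at 0.30; with 20 per arm the type I error is 0.250 at 50% success and at most 0.298; power is 0.865 for 75% vs 50%.* It needs the same 40 patients. It changes the go/no-go rule, so it needs an amendment. The false-go rate at 50% success rises from 0.215 to 0.250, the test is less familiar, and two-patient leads near 50% success (10 vs 8, 11 vs 9, 12 vs 10) still fail while most others pass.
2. **Keep Fisher.** Suggested wording: *Fisher's one-sided exact test, nominal threshold 0.30; with 20 per arm the attained type I error is at most 0.215 and power is 0.80 for 75% vs 50%.* This costs one sentence and, if Fisher was intended, changes no decision. It is a reasonable choice if the team prefers the stricter rule and accepts leaving about 6 points of power unused.

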APPENDIX I
"REGION GROWING" INSTRUCTIONS FOR ECLIPSE

- 1) After import MRI images into Eclipse, go to "**Contouring**", select the MRI image which you will use to contour, and double click. This should bring the selected image thumbnail to the top left portion of the screen.

Right Click on the image at the top left of the screen and select new structure. Under Label, type "Control Region". Under ID, type the name (example Edema_Pretx) and press "Create".

- 2) On the right taskbar, select "Imaging Threshold" and type in a range to encompass the hyperintense edema (Example Range 1000-2500). Click "Select VOI" and make the box encompass the area of edema at risk. Click Apply. If the range is not accurate, it may be modified.
- 3) This will create an ROI for edema that should then be modified by the physician to take out unnecessarily contoured structures (i.e. bone, calcifications, areas that are not consistent with edema. Edema should not include the appreciable gross tumor volume.
- 4) Select "Post Processing" and press "Apply to remove very small contoured areas.
- 5) Right click on the ROI at the top left and click "properties" to view and record the volume in cc's.

Separate ROIs maybe created for the gross tumor volume which should be manually contoured.

APPENDIX II
GLUCOSE MONITORING INSTRUCTIONS

HOW OFTEN SHOULD I CHECK MY BLOOD SUGAR?

4 Times a Day (the study team will let you know if you can check less often than 4 times a day):

1. Before breakfast (fasting)
2. Before lunch
3. Before dinner
4. At bedtime

More Often:

- When you feel symptoms of low or high sugars, illness, or stress
- When your doctor changes your medicine doses
- If you are more physically active than usual
- If you are pregnant or planning to become pregnant

Please write the results down in your blood glucose log and take it to all your clinic visits.

Why Should I Check My Blood Sugar?

Knowing what your blood sugar is:

- Helps you make decisions about how to eat, exercise, or take my medicine
- Lets you and us know if my any treatment needs to be changed

What Should my Blood Sugar be?

Before Meals: 80-130

2 Hours After Meals: Less than 180

Bedtime: 90-150

Less than 80 is too low.

If the patient is having symptoms that they think are related to their blood sugar level or if their blood sugar level is below 80, they will be instructed to check their fingerstick blood glucose level again and begin to try the items listed in "**Low Blood Sugar Interventions**", described in **Section 5.4.1.1 and Appendix IV**. If "**Low Blood Sugar Interventions**" does not cause the blood sugar to rise above 80 after drinking or eating, or if their symptoms are not improving or worsening, the patient will be instructed to contact the study team and/or call 911 for emergency services.

APPENDIX III
HOW TO CHECK BLOOD GLUCOSE

MONITORING

How to Check Your Blood Glucose

(page 1 of 2 pages)

The only way to know how well your diabetes management plan is working is to check the amount of glucose that is in your blood throughout the day, every day.

Follow these steps when you check your blood glucose.

Step 1. Gather your supplies:

- home blood glucose meter
- testing strips
- **lancing device**, which makes it easier to stick your finger or forearm
- **lancet**, a tiny needle
- **sharps container**, a special plastic bottle in which you dispose of your lancets
- blood glucose record

Step 2. Wash and dry your hands, and the area you are lancing.

Step 3. Make sure you have enough blood in the area you are lancing.

For your finger, hang your hand at your side for a few seconds, or shake your hand several times. You can also squeeze the hand you are using with your other hand – in one motion from the palm of your hand to the fingertip. If you are lancing your forearm, rub it gently.

APPENDIX III – Continued...
HOW TO CHECK BLOOD GLUCOSE

MONITORING

How to Check Your Blood Glucose

(page 2 of 2 pages)

Step 4. Set up your meter.

Turn on your meter, if required. Most meters turn on when you insert a testing strip. Insert your testing strip as directed.

Step 5. Lance your finger or forearm.

[figure not shown]
Use your lancing device to get a drop of blood from your finger or forearm. The side of your finger hurts less than the finger tip. If you are lancing your arm, use the area closer to your elbow than your wrist.

Step 6. Collect the blood on the testing strip.

Step 7. Read your results.

Step 8. Write the results in your blood glucose record.

There are many different meters available. Not every meter allows you to use your forearm. Use your meter as directed by the manufacturer. If you have questions or concerns, call the toll-free number found directly on the meter.

APPENDIX IV
HOW TO MANAGE LOW BLOOD SUGAR

Low Blood Sugar Interventions

[figure not shown]
If you develop any of these symptoms during your time on study, please try:

- Drinking $\frac{1}{2}$ cup of juice or soda
- Eating a few pieces of candy
- Taking 3 or 4 glucose tablets

If it will be more than an hour until meal time, try eating a snack that is high in starch. Snacks that are high in starch include:

- Crackers
- Bread
- Cookies

Symptoms include:

APPENDIX V
BLOOD GLUCOSE LOG

Day / Date		Breakfast		Lunch		Dinner		Bedtime	Comments
		Before	After	Before	After	Before	After		
Monday Date:	Blood Glucose								
	Time								
Tuesday Date:	Blood Glucose								
	Time								
Wednesday Date:	Blood Glucose								
	Time								
Thursday Date:	Blood Glucose								
	Time								
Friday Date:	Blood Glucose								
	Time								
Saturday Date:	Blood Glucose								
	Time								
Sunday Date:	Blood Glucose								
	Time								

APPENDIX VI
MEDICATION ADMINISTRATION LOG

In the appropriate area please indicate the time that you took your medication. Please remember to take your medication twice a day – in the morning with breakfast and in the evening with dinner. If you miss a dose, please do not make it up, just indicate it on this log by putting an X in the box where you missed your dose.

Please do not hesitate to call the research office if you have any questions or concerns.

Day	Date	Time	
		Morning Dose (AM)	Evening Dose (PM)
Monday			
Tuesday			
Wednesday			
Thursday			
Friday			
Saturday			
Sunday			
Monday			
Tuesday			
Wednesday			
Thursday			
Friday			
Saturday			
Sunday			
Monday			
Tuesday			
Wednesday			
Thursday			
Friday			
Saturday			
Sunday			

Signature: _____ Date: _____

APPENDIX VII
CTCAE version 4.0 and Toxicity Criteria

This study will utilize **NCI Common Terminology Criteria for Adverse Events (CTCAE) version 4.0 for toxicity and Adverse Event Reporting**. A **grading** (severity) scale is provided for each Adverse Event (AE) term. A copy of the CTCAE version 4.0 can be downloaded from the CTEP web site at: http://ctep.cancer.gov/protocolDevelopment/electronic_applications/ctc.htm. All investigators and study staff have access to a copy of the CTCAE version 4.0. Also, see Sections 5.3 and 7.3 for additional information.

An **Adverse Event (AE)** is any unfavorable and unintended sign (including an abnormal laboratory finding), symptom, or disease temporally associated with the use of a medical treatment or procedure that may or may not be considered related to the medical treatment or procedure.

Grade refers to the severity of the AE. The CTCAE displays Grades 1 through 5 with unique clinical descriptions of severity for each AE based on this general guideline:

- **Grade 1:** *Mild; asymptomatic or mild symptoms; clinical or diagnostic observations only; intervention not indicated.*
- **Grade 2:** *Moderate; minimal, local or noninvasive intervention indicated; limiting age-appropriate instrumental Activities of Daily Living (ADL).*
- **Grade 3:** *Severe or medically significant but not immediately life-threatening; hospitalization or prolongation of hospitalization indicated; disabling; limiting self care Activities of Daily Living (ADL).*
- **Grade 4:** *Life-threatening consequences; urgent intervention indicated.*
- **Grade 5:** *Death related to AE.*

Adverse Event	GRADE				
	1	2	3	4	5
Hypoglycemia	<LLN – 55mg/dL; <LLN – 3.0 mmol/L	<55-40 mg/dL; <3.0-2.2 mmol/L	<40-30 mg/dL; <2.2-1.7 mmol/L	<30 mg/dL; <1.7 mmol/L; life-threatening consequences; seizures	Death

Definition: A disorder characterized by laboratory test results that indicate a low concentration of glucose in the blood.

APPENDIX VIII
STUDY SCHEDULE OF EVENTS
PILOT PORTION

Assessments	Pretreatment		Treatment		Post Treatment		
	≤ 60 days prior to registration	≤ 14 days prior to registration	5-9 days prior to SRS	Day of SRS	7 days (1 wk) post SRS (± 3 days)	30 days (1 mo) post SRS (-5 to +10 days)	90 days (3 mo) post SRS (-10 to +14 days)
History and physical with neurological exam		C ¹				C	C
Documentation of steroid use		C	C	C	C	C	C
Glucose education / supply distribution ²			R				
Fingerstick Glucose by patient			R ³	R ³	R ⁴	R ⁵	
Fingerstick Glucose by nurse/research team member			R		R	R	
Review of Medication and Glucose Logs					R	R	
CBC w/ diff and CMP including LFTs		C			C	C	C
Start Glyburide (should start at least 5 days prior to SRS)			R				
Stop Glyburide						R ⁵	
Pregnancy test (if applicable)		C					
Contrast-enhanced MRI of the brain	C ⁶					C ⁶	C ⁶
AE evaluation					C	C	C

C = Conventional Care. **R** = Research Related.

1. Baseline history and physical exam must include height and weight.
2. The patient will be supplied with a blood glucose monitor, a fingerstick glucose device, medication/blood glucose logs, and handouts for education purposes. The patient will be educated on how to measure and record blood glucose values. See Appendices II-VI.
3. Fingerstick glucose draws to be done by the patient 4 times a day (in the morning before breakfast (fasting), before lunch, before dinner, and before bed) beginning at least 5 days prior to SRS (the same day as starting glyburide) and continuing for at least 1 week after SRS.
4. Fingerstick glucose draws to be done by the patient once a day only if the patient doesn't have a concerning or serious toxicity at the 1 week post SRS visit. See Section 5.3.1 for further details.
5. The last dose of glyburide is taken on the evening of the day the 1 month post SRS MRI is done. Fingerstick glucose draws also discontinue at the same time as glyburide discontinuation.
6. MRI with and without contrast. T1-weighted, T2 and/or FLAIR MRI of the brain (maximum slice thickness 5mm). FLAIR imaging is preferred. Pretreatment MRI to be done within 21 days of SRS.

APPENDIX VIII *continued*
STUDY SCHEDULE OF EVENTS
RANDOMIZED PORTION

Assessments	Pretreatment		Treatment		Post Treatment		
	≤ 60 days prior to registration	≤ 14 days prior to registration	5-9 days prior to SRS	Day of SRS	7 days (1 wk) post SRS (± 3 days)	30 days (1 mo) post SRS (-5 to +10 days)	90 days (3 mo) post SRS (-10 to +14 days)
History and physical with neurological exam		C ¹				C	C
Documentation of steroid use		C	C	C	C	C	C
Glucose education / supply distribution ²			R				
Fingerstick Glucose by patient			R ³	R ³	R ⁴		
Fingerstick Glucose by nurse/research team member			R		R	R	
Review of Medication and Glucose Logs					R	R	
CBC w/ diff and CMP including LFTs		C			C	C	C
Start Investigational medication (should start at least 5 days prior to SRS)			R				
Stop Investigational medication						R ⁵	
Pregnancy test (if applicable)		C					
Contrast-enhanced MRI of the brain	C ⁶					C ⁶	C ⁶
AE evaluation					C	C	C

C = Conventional Care. **R** = Research Related.

1. Baseline history and physical exam must include height and weight.
2. The patient will be supplied with a blood glucose monitor, a fingerstick glucose device, medication/blood glucose logs, and handouts for education purposes. The patient will be educated on how to measure and record blood glucose values. See Appendices II-VI.
3. Fingerstick glucose draws to be done by the patient once a day beginning at least 5 days prior to SRS (the same day as starting investigational medication) and continuing for at least 1 week after SRS. See Section 5.4.2 for further details.
4. Fingerstick glucose draws to be done by the patient may be stopped only if the patient doesn't have a concerning or serious toxicity at the 1 week post SRS visit. See Section 5.3.2 for further details.
5. The last dose of the investigational medication is taken on the evening of the day the 1 month post SRS MRI is done.

6. MRI with and without contrast. T1-weighted, T2 and/or FLAIR MRI of the brain (maximum slice thickness 5 mm). FLAIR imaging is preferred. Pretreatment MRI to be done within 21 days of SRS.
